## STUDY PROTOCOL

### 1. Project Title:

Chronic Pain in Patients Undergoing Mastectomy: The Difference Between Pectoral Nerve Block (PECS I-II) and Erector Spinae Plane (ESP) Block

### 2. Rationale of the Project:

Breast cancer is the most commonly diagnosed cancer among women and remains a leading cause of cancer-related mortality. Globally, it ranks second only to lung cancer in incidence, with both accounting for approximately 11.6% of all diagnosed cancer cases (1). In the United States, the lifetime risk for a woman to develop breast cancer is estimated at 13%, indicating that one in eight women will be affected during their lifetime (2).

Over the past two decades, significant advances in breast cancer research have markedly improved our understanding of the disease, enabling the development of more effective and less toxic treatments. Enhanced public awareness and improved screening methods have facilitated early detection at stages amenable to surgical resection and curative therapy. Consequently, survival rates—especially among younger women—have substantially improved (3).

Surgical treatment of breast cancer includes both conservative and non-conservative approaches. Conservative surgeries account for approximately 40% of all procedures, with quadrantectomy being the most commonly performed among them (4). However, surgical treatment may lead to various complications, including chronic postoperative pain (5).

Post-mastectomy pain syndrome (PMPS) is typically defined as chronic pain in the breast or chest wall persisting for at least three months following cancer treatment. It arises after surgical interventions for breast cancer and is believed to result from primary nerve injury or dysfunction of the nervous system (6,7). Clinically, it presents with features of neuropathic pain such as burning, tingling, stabbing, or shooting sensations, and hyperesthesia (8). Although no standardized diagnostic criteria exist, the estimated incidence ranges from 40% to 50% (7,9), with about half of affected women reporting moderate to severe pain (10).

Younger age (<40 years) has been identified as a major risk factor, though age does not appear to correlate with the intensity of reported pain (10). Severe acute postoperative pain is also considered a predictive factor for the development of chronic pain. Furthermore, radiotherapy to the breast and/or axillary region has been associated with an increased risk of chronic pain when compared to patients who did not receive radiation therapy (11). Among surgical contributors to PMPS, extensive axillary lymph node dissection is significant due to the increased risk of intercostobrachial nerve injury, which may lead to neuropathic pain (12,13).

Strategies aimed at reducing the risk of PMPS emphasize optimizing perioperative pain management. Techniques such as paravertebral, erector spinae plane (ESP), and pectoral

nerve blocks are routinely applied in appropriate surgical cases to reduce postoperative pain and minimize the risk of chronic pain development in many centers, including ours (14). Both ESP and PECS I-II blocks have demonstrated efficacy and are associated with low complication rates (14,15,16).

In our study, we aim to observe the incidence of chronic pain following mastectomy in patients who have received either a pectoral nerve block (PECS I-II) or an erector spinae plane (ESP) block as part of their pain management strategy. These blocks will be administered by the attending anesthesiologist after general anesthesia induction and prior to the initiation of surgery. The choice and timing of the block will be determined independently by the anesthesiologist and not influenced by the study team. The primary outcome of this study is to compare the incidence of chronic postoperative pain between the two groups. The secondary outcome is to assess the impact of these blocks on acute postoperative pain levels and opioid requirements.

### **3. Materials and Methods of the Study**

#### **3.1 Study Setting**

Department of Anesthesiology and Reanimation, Hacettepe University.

#### **3.2 Study Timeline**

April 15, 2024 – August 15, 2024.

#### **3.3 Study Population, Sample Size, and Study Groups**

Following approval by the Hacettepe University Ethical Committee, patients aged 18 to 65 years, classified as ASA physical status I-II, and scheduled to undergo elective modified radical mastectomy or simple mastectomy with sentinel/axillary lymph node dissection under general anesthesia at Hacettepe University Hospitals between April 15 and May 15, 2024, will be included. Patients must have already been scheduled to receive either an ESP or PECS I-II block for postoperative pain management independently of the study. A total of 40 patients will be enrolled, with 20 in each group at least. Patients with coagulation disorders, allergies to local anesthetics, obesity ( $BMI > 35 \text{ kg/m}^2$ ), infection at the injection site, pre-existing neurological deficits, or unwillingness to participate, as well as those with failed blocks, will be excluded. The decision to perform blocks is made by the responsible anesthesiologist and will not be influenced by the study team.

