#### **3.5. Research Method and Data Collection Tools:**

Upon admission to the operating room, non-invasive arterial blood pressure, electrocardiogram, and peripheral oxygen saturation monitoring will be conducted before

the induction of general anesthesia. This is the routine monitoring protocol applied prior to anesthesia. All patients will receive standard general anesthesia and standard ventilation modes. The research team will not intervene in the anesthesia procedure.

According to the standard anesthesia practice in these cases, anesthesia induction is performed with propofol (1.5–2.5 mg/kg), rocuronium (0.4–0.6 mg/kg), and fentanyl (1–2 mcg/kg), with a 50% oxygen-air mixture. Standard ventilator settings are applied.

Anesthesia maintenance consists of 2% sevoflurane with 50% oxygen-air mixture. These practices are routine in our operating theater and are not specifically designed for this study. In the event of any non-routine requirement, decisions will be made by the responsible anesthesiologist, without any intervention from the research team. The study will commence after anesthesia induction and block application.

Following the induction of general anesthesia, the responsible anesthesiologist will independently administer either the PECS I-II or ESP block prior to surgical incision. The choice of block will not be influenced by the study and will be determined solely by the anesthesiologist, regardless of group distribution. The research team will not interfere in the selection or method of block administration.

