#### Postoperative Pain Control:

In addition to routine 3×1000 mg IV paracetamol, rescue analgesia with IV tramadol (0.5 mg/kg) will be administered as needed. These practices are part of our standard multimodal analgesia protocol and not specific to the study. After discharge, patients will be transitioned to oral paracetamol, with a recommendation of 3×500 mg daily for one month if necessary

Postoperative follow-up interviews will be conducted by a study assistant. Time of initial pain, and whether rescue analgesia was needed within the first 24 hours, will be recorded. Pain levels will be assessed at 20 minutes, 6 hours, and 1 day postoperatively using the Numerical Rating Scale (NRS). If NRS >0, the DN4 (Douleur Neuropathique 4) questionnaire will be administered. At the 3-month follow-up, patients will be contacted via phone and evaluated with the DN2 and SF-12 questionnaires. No blood samples or invasive procedures will be performed for research purposes.

The NRS is a simple and widely used 0–10 scale to assess pain severity, from "0 = no pain" to "10 = worst imaginable pain." It is considered valid and reliable. The DN4 questionnaire, administered by clinicians, includes 10 items to evaluate neuropathic pain, with a sensitivity of 83% and specificity of 90%. A score ≥4 indicates neuropathic pain. The SF-12 Quality of Life questionnaire, validated in Turkish, consists of 12 items and is used to assess overall health status and quality of life.

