#### **3.6. Data Collection**

Following ethics committee approval, eligible patients aged 18–65 years scheduled for elective modified radical mastectomy between April 15 and May 15, 2024, at Hacettepe University Hospital, who had already been assigned ESP or PECS I-II blocks for postoperative pain control independent of the study, will be enrolled. The study is observational, and no interventions will be made regarding clinical treatment decisions. Patient demographic data (ASA score, age, sex, weight, height, BMI, comorbidities) and intraoperative details will be recorded

Postoperative data within the first 24 hours will be collected via face-to-face interviews and entered into the follow-up and DN4 forms. At 3 months, DN2 and SF-12 questionnaires will be administered via telephone interviews

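### Does enrolling 40 patients, with nothing added for those not reached at 3 months, leave the primary comparison short?

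*Combined protocol and SAP*

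**What the plan says.** Section 3.3 fixes the number: "A total of 40 patients will be enrolled, with 20 in each group at least". It limits surgery to one month, for patients operated on "under general anesthesia at Hacettepe University Hospitals between April 15 and May 15, 2024, will be included". Section 3.5 starts each patient's participation once the block is in place: "The study will commence after anesthesia induction and block application".

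Section 2 names the primary outcome: "The primary outcome of this study is to compare the incidence of chronic postoperative pain between the two groups". Its background text describes the post-mastectomy syndrome as "chronic pain in the breast or chest wall persisting for at least three months following cancer treatment".

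After the first 24 hours one contact remains. The text on postoperative pain control says "At the 3-month follow-up, patients will be contacted via phone and evaluated with the DN2 and SF-12 questionnaires", and section 3.6 repeats it: "At 3 months, DN2 and SF-12 questionnaires will be administered via telephone interviews". Section 3.2 gives the timeline as "April 15, 2024 – August 15, 2024".

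Section 3.7 compares categorical outcomes by chi-square or Fisher's exact test. No section gives a loss allowance, a call window, a number of attempts, or a rule for patients not reached. Nor does any section give a power, an effect size or a derivation for the 40.

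**The concern.** Read literally, 40 in total with at least 20 per group permits only a 20/20 split, so one unreached patient leaves a group at 19. Section 2 names no instrument or time for the primary outcome, but no contact other than the 3-month call could supply it. A loss shows only when calls begin, and by then enrolment has long closed. Calling early would not help, because the condition is described as lasting at least three months. For a patient operated on May 15 the call falls due on the last day of the timeline.

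Two things would be at stake. One is precision, in a study that is already small. The other is bias: at 20 per group, each unreached patient leaves up to 1/20 = 5 points of the difference undetermined, and with no written rule the treatment of those patients could be settled after the data are seen.

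**Working it through.** **Inputs from the documents.** 40 patients, 20 per group (3.3); surgery April 15 to May 15, 2024 (3.3, 3.6); study end August 15, 2024 (3.2); background incidence 40% to 50% (section 2), of which I use the midpoint, 45%, in both groups. **Assumptions.** Loss of 5%, 10% or 20%, independent between patients; three calendar months to the call. The 40 cannot be reproduced, because the plan gives no inputs for it.

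**1. Dates.** The first call is due April 15 + 3 months = July 15, which is 61 days after May 15. The last is due May 15 + 3 months = August 15. Time left before the stated end runs from 31 days down to 0, and is under 14 days for 10 of the 23 weekdays in the surgery window. Every due date fits.

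**2. Chance that all 40 are reached,** (1 − loss)^40:
- 5%: 0.95^40 = 12.9%
- 10%: 0.90^40 = 1.5%
- 20%: 0.80^40 = 0.01%

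Some loss is therefore likely. The question is what it costs.

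**3. Precision.** Half-width = 1.96 × √(0.45 × 0.55 × 2/n), with n reached per group:

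| Loss | n reached | Half-width (points) | Widening |
|---|---|---|---|
| none | 20 | ±30.8 | – |
| 5% | 19 | ±31.6 | 0.8 |
| 10% | 18 | ±32.5 | 1.7 |
| 20% | 16 | ±34.5 | 3.6 |

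**4. Unknown outcomes.** Take equal observed incidence and m unreached of N per group. Counting the unreached as all in pain in one group and none in the other, then the reverse, gives a range of ±m/N.
- 2 of 20: 8/18 in each group gives 8/20 − 10/20 = −10 points to +10 points.
- 4 of 20: 7/16 in each group gives −20 to +20 points.

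**5. Would more patients help?** For at least an 80% chance that 20 or more are reached in both groups at 10% loss, each group needs 24: P(Bin(24, 0.9) ≥ 20)² = 0.837. That is 8 more patients. The expected number unreached is then 2.4 of 24, and 2.4/24 = 10%, so the range in step 4 stays at ±10 points. It depends on the loss rate and not on N. At 20% loss the same criterion gives 28 per group, and 5.6/28 = 20%, again unchanged.

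**6. Side effect of closing each group at 24.** If blocks are chosen 60:40 (an assumption), filling both groups takes about 60 eligible patients, of whom about 12 would be turned away. With full follow-up, 24/24 gives 1.96 × √(0.2475 × 2/24) = ±28.1 points. Keeping all of them, 36/24, gives 1.96 × √(0.2475 × (1/36 + 1/24)) = ±25.7. The 2.5 points given up exceed the 1.7 that a 10% loss costs.

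**7. Sensitivity of the test.** Fisher's exact test on 11/20 versus 4/20 gives p = 0.048. If two patients in the first group are not reached:
- both had pain, 9/18: p = 0.087
- one had pain, 10/18: p = 0.042
- neither had pain, 11/18: p = 0.019

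Even from a result placed on the threshold, significance is lost in one of the three cases.

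**The case for a change.** The strongest case for a change leaves the sample size alone. It asks for a call window opening no earlier than 3 months after surgery, a number of attempts, permission to finish calls after August 15, a stated denominator, and a best-case/worst-case range for the difference. None of this needs another patient, and writing it down beforehand would remove any suspicion that the denominator was chosen to suit the result. The silence is real: section 3.7 has no missing-outcome rule, and the last patient has no spare day before the stated end.

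What stands is that these details would be better written than unwritten. What does not stand is that their absence makes a stated rule wrong. Section 3.2 gives a study timeline and sets no last-call or data-lock date, so a repeat call a few days late breaches nothing. The protocol fixes a time point and does not limit attempts. With a single time point, a count and a two-group test, analysing those reached and reporting how many were not is what an analyst would ordinarily do. The best-case/worst-case range would be a useful extra sensitivity report, but it corrects nothing in the plan.

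It may also be said that 20 per group is the intended evaluable number. The text does not say so: it counts enrolment, and no power or effect size marks 20 as a threshold. The words allowing at least 20 per group can also be read as a floor, so it is too firm to say that no patient is spare. That the 40 has no stated basis is a wider matter, and a loss allowance would not settle it.

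**Conclusion.** The facts are right, but no change is called for. Losses are likely and cannot be replaced within the dates, as in any cohort whose follow-up is longer than its accrual period. Their cost in precision is 0.8 to 3.6 points on a half-width of about 31, for assumed losses of 5% to 20% and 45% incidence. The larger uncertainty, about ±10 points at 10% loss and ±20 at 20%, follows the loss rate, and enrolling more patients leaves it where it is. The plan states no evaluable number or power that is missed. The unwritten call and reporting details are ones that a study team fills sensibly, and the timeline leaves room to do so. The conclusion rests on the assumed loss rates and on the inference that the 3-month call supplies the primary outcome.

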#### **3.4 Study Type**

Prospective Cohort Study

#### **3.5. Research Method and Data Collection Tools:**

Upon admission to the operating room, non-invasive arterial blood pressure, electrocardiogram, and peripheral oxygen saturation monitoring will be conducted before

the induction of general anesthesia. This is the routine monitoring protocol applied prior to anesthesia. All patients will receive standard general anesthesia and standard ventilation modes. The research team will not intervene in the anesthesia procedure.

According to the standard anesthesia practice in these cases, anesthesia induction is performed with propofol (1.5–2.5 mg/kg), rocuronium (0.4–0.6 mg/kg), and fentanyl (1–2 mcg/kg), with a 50% oxygen-air mixture. Standard ventilator settings are applied.

Anesthesia maintenance consists of 2% sevoflurane with 50% oxygen-air mixture. These practices are routine in our operating theater and are not specifically designed for this study. In the event of any non-routine requirement, decisions will be made by the responsible anesthesiologist, without any intervention from the research team. The study will commence after anesthesia induction and block application.

Following the induction of general anesthesia, the responsible anesthesiologist will independently administer either the PECS I-II or ESP block prior to surgical incision. The choice of block will not be influenced by the study and will be determined solely by the anesthesiologist, regardless of group distribution. The research team will not interfere in the selection or method of block administration.

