#### ESP Block Protocol:

The patient is placed in lateral decubitus position with the surgical side up. The ultrasound probe is placed longitudinally at the level of the T4–5 spinous processes and then moved laterally toward the surgical side. The transverse process and overlying trapezius, rhomboid, and erector spinae muscles are visualized. Under aseptic conditions, the block needle is inserted at a 30–40° crano-caudal angle, passing through the trapezius, rhomboid, and erector spinae muscles. After confirming placement with 2–3 mL isotonic saline, 20–30 mL of 0.25% bupivacaine is injected between the erector spinae muscle and transverse process.

Both PECS I-II and ESP blocks will be performed under ultrasound guidance, and the needle position will be verified through anatomical visualization and hydrodissection. Blocks will

be considered successful if applied by the responsible anesthesiologist under these conditions.

At the end of surgery, maintenance agents will be discontinued, and intravenous sugammadex will be administered to reverse muscle relaxation, dosed according to patient weight. About 30 minutes prior to the end of surgery, 1000 mg intravenous paracetamol will be routinely administered for analgesia. Extubation will occur after the patient regains spontaneous breathing and emerges from anesthesia. This is standard procedure and will not be modified for the study. No interference will occur with decisions regarding anesthesia drugs, ventilation methods, or intubation technique.

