### **3.7. Data Analysis**

Normality of numeric data will be assessed using the Shapiro-Wilk test. Data following a normal distribution will be compared between two independent groups using the Student's t-test. Non-normally distributed data will be analyzed using the Mann-Whitney U test. For three-group comparisons, one-way ANOVA will be used if parametric assumptions are met; otherwise, the Kruskal-Wallis H test will be applied. Descriptive statistics will include mean  $\pm$  standard deviation for normally distributed data, or median (minimum–maximum) for non-normal data. Categorical variables will be summarized as counts (percentages), and group comparisons will be performed using chi-square or Fisher's exact test as appropriate. A p-value  $<0.05$  will be considered statistically significant in all analyses.

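### The operator chooses and gives the block but is neither named for recording nor used in the analysis, so an operator effect could be reported as a block effect

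*Combined protocol and SAP*

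**What the plan says.** Section 3.5 gives the choice of block to one person: "The choice of block will not be influenced by the study and will be determined solely by the anesthesiologist, regardless of group distribution". That person also delivers it: "the responsible anesthesiologist will independently administer either the PECS I-II or ESP block prior to surgical incision". Technique is left open ("The research team will not interfere in the selection or method of block administration"), and so are departures from routine anaesthesia ("In the event of any non-routine requirement, decisions will be made by the responsible anesthesiologist").

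The routine itself leaves some latitude. Induction fentanyl is given as 1–2 mcg/kg in section 3.5. The ESP volume is 20–30 mL, while the PECS volumes are fixed at 10 mL and 20 mL. Under the ESP Block Protocol heading, blocks of both types will "be considered successful if applied by the responsible anesthesiologist under these conditions", so there is no independent check of block quality.

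Section 3.6 lists what is collected: "Patient demographic data (ASA score, age, sex, weight, height, BMI, comorbidities) and intraoperative details will be recorded". The intraoperative entry is not defined, and the operator is not named.

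For the primary outcome, the incidence of chronic pain, the applicable sentence of section 3.7 is: "Categorical variables will be summarized as counts (percentages), and group comparisons will be performed using chi-square or Fisher's exact test as appropriate". Numeric outcomes get a t-test or Mann-Whitney test. The section has no operator term, stratification, regression or clustered variance.

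**The concern.** In a cohort where the clinician selects the exposure, that clinician can be a common cause of exposure and outcome. Skill, volume used and intraoperative opioid habits may differ between anesthesiologists. Section 2 itself names severe acute postoperative pain as a predictor of chronic pain, so there is a plausible route from operator to primary outcome. Operator skill and habit are not patient characteristics, so adjusting for age, BMI or comorbidity would not remove their influence.

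Two consequences follow if operators favour one block. The ESP versus PECS I-II contrast becomes partly a contrast between two sets of operators. And patients of one operator resemble each other, so tests that assume independence can give p-values that are too small. How far either applies depends on how blocks were distributed over operators, which the plan as written would not report.

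**Working it through.** The plan has no figure of its own to reproduce here: section 3.3 gives 40 patients, at least 20 per group, without effect size, power, number of operators or ICC.

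**Inputs from the documents.** 20 patients per group (3.3). Background incidence 40% to 50% (section 2), taken at 45% in both groups. Chi-square or Fisher at 0.05 (3.7), taken as two-sided.

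**Assumptions.** ICC (ρ) of 0.05, 0.10 and 0.20; the number of operators; the split of blocks within operator.

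**Variance formula.** If operator j treats a_j patients with one block and b_j with the other, the variance of the difference in proportions, relative to independent patients with 20 per group, is

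DE = (1 − ρ) + ρ × Σ(a_j − b_j)² / 40.

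- 2 operators per group, one block each (10 patients each): Σ = 4 × 10² = 400, so DE = 1 + 9ρ.
- 4 per group, one block each (5 each): Σ = 8 × 5² = 200, so DE = 1 + 4ρ.
- 10 per group, one block each (2 each): Σ = 20 × 2² = 80, so DE = 1 + ρ.
- 4 operators in all, 80:20 (8 and 2): Σ = 4 × 6² = 144, so DE = 1 + 2.6ρ.
- 8 operators in all, 80:20 (4 and 1): Σ = 8 × 3² = 72, so DE = 1 + 0.8ρ.
- Equal use: Σ = 0, so DE = 1 − ρ. With 4 operators at 60:40 (6 and 4), Σ = 4 × 2² = 16 and DE = 1 − 0.6ρ. Both are below 1.

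**Simulated false positives.** Beta-binomial operator effects, no block effect, 40,000 runs per setting, uncorrected chi-square. Without clustering the rate is about 4.4% (Fisher about 2.2%).

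| Pattern of use | DE at ρ = 0.05 / 0.10 / 0.20 | Chi-square, % | Fisher, % |
|---|---|---|---|
| Both blocks, 50:50 or 60:40 | below 1 | about 3–4 throughout | not above 2.2 |
| 8 operators, 80:20 | 1.04 / 1.08 / 1.16 | 4.9 / 5.4 / 6.8 | 2.4 / 2.8 / 3.5 |
| 10 per group, one block each | 1.05 / 1.10 / 1.20 | 5.1 / 5.7 / 6.8 | 2.5 / 2.9 / 3.9 |
| 4 operators, 80:20 | 1.13 / 1.26 / 1.52 | 6.1 / 8.2 / 11.9 | 3.1 / 4.3 / 7.2 |
| 4 per group, one block each | 1.20 / 1.40 / 1.80 | 6.9 / 9.4 / 14.3 | 3.5 / 5.4 / 9.2 |
| 2 per group, one block each | 1.45 / 1.90 / 2.80 | 9.7 / 15.6 / 25.6 | 5.7 / 10.5 / 19.0 |

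Repeat runs agree to about half a percentage point.

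**Effective sample size.** At ρ = 0.10 with one block per operator, the 20 patients in a group are worth 20/1.9 = 10.5 (2 operators), 20/1.4 = 14.3 (4) or 20/1.1 = 18.2 (10).

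**Scale of the ICC.** The table puts ρ on the observed yes/no scale. On a latent normal scale, ρ = 0.10 gives chi-square rates of 11.5% (2 per group), 7.3% (4 per group) and 5.2% (10 per group). The ordering is the same and the inflation is smaller.

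**The case against.** The strongest reply is that nothing in the documents shows that operators favour one block. Section 2 says these techniques are used routinely in suitable surgical cases, which fits choice by case as well as choice by operator. One department and a one-month enrolment window do not fix the number of operators. With balanced use the planned tests are slightly conservative, and where Fisher's test is used the inflation is smaller. This stands, and it is why the size is given as a range.

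A reader might infer that block and operator cannot be separated in this study. The documents do not support that: it would need most operators to use a single block, which is not stated. A reader might also infer that the matter could never be examined later. That goes too far, because the undefined intraoperative entry in section 3.6 may include the operator and the anaesthesia record may identify that person. Even so, section 3.7 would make no use of the information.

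Two further steps are tempting and not justified. Nothing in the documents links the surgeon to the choice of block, so this point gives no case for a surgeon identifier. An obligatory operator-clustered interval would also serve poorly where it is most needed. With 2 operators per group it has 2 degrees of freedom, and at ρ = 0.10 its median half-width is about 78 percentage points (about 44 with 4 per group), against 1.96 × √(2 × 0.45 × 0.55 / 20) = 31 points unclustered.

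That the study is observational is no answer. It is a reason to record who assigned the exposure, and doing so leaves clinical choice untouched.

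**Conclusion.** The point holds in conditional form. It is established that one clinician chooses and gives the block, that the operator is not named for recording, and that no planned analysis uses the operator. If operators favour one block, an operator effect would be reported as a block effect.

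The consequence runs from none (roughly equal use of both blocks) to severe (2 single-block operators per group, chi-square false positives 10–26%). The range rests on the assumed 45% incidence, 20 per group, ICC 0.05 to 0.20 and the assumed patterns of use. The documents do not say where in it this study lies. That uncertainty justifies recording and tabulating the operator; it does not support a claim that the result is already uninterpretable.

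**What to change.** In section 3.6, add a coded identifier for the anesthesiologist who performed the block, with trainee or specialist grade, taken from the anaesthesia record (assuming the record holds it).

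In section 3.7:

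- Report a block-by-operator table.
- Add an operator-stratified sensitivity result for chronic pain only where enough operators used both blocks, with what counts as enough fixed before outcomes are examined.
- If most operators used one block, state that the difference cannot be attributed to the block rather than to the operator.

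The cost is one extra coded entry per patient with its grade, one table, at most one sensitivity analysis, and possibly a weaker conclusion. No clinical decision changes.
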